10.1.7.2.2 Every 2 weeks (Biweekly)

The following will be performed every 2 weeks starting at Week 3 (W3, W5, W7, W9, W11, W13, W15, W17, W19, W21, W23, W25, W27, W29, W31, W33, W35, W37, W39, W41, W43, W45, W47, W49, W51, W53, W55, W57, W59, W61, W63, W65, W67, W69, W71, W73, W75, W77, W79, W81, W83, W85, W87, W89, W91, W93, W95 & W97):

- IRT contact for treatment kits allocation;
- Vital signs (before, during, and following infusion);
- Infusion of avalglucosidase alfa;
- AE collection;
- Prior/concomitant medications.

10.1.7.2.3 Every 4 weeks

The following assessments will be performed every 4 weeks (W5, W9, W13, W17, W21, W25, W29, W33, W37, W41, W45, W49, W53, W57, W61, W65, W69, W73, W77, W81, W85, W89, W93 & W97):

- IRT contact for treatment kits allocation;
- Vital signs (before, during, and following infusion);

- Infusion of avalglucosidase alfa;
- AE collection;
- Prior/concomitant medications;
- Body weight;
- Urine pregnancy test (females of childbearing potential only);
- Biochemistry;
- ADAs (with neutralizing antibodies in ADA-positive patients) (monthly through Week 73, then at W97 only).

10.1.7.2.4 Every 12 weeks until W73 and at W97

The following assessments will be performed every 12 weeks until W73 and at W97 (W13, W25, W37, W49, W61, W73 & W97):

- IRT contact for treatment kits allocation;
- Vital signs (before, during, and following infusion);
- Infusion of avalglucosidase alfa;
- AE collection;
- Prior/concomitant medications;
- Body weight;
- Urine pregnancy test (females of childbearing potential only);
- Hematology, biochemistry, and urinalysis;
- ADAs (with neutralizing antibodies in ADA-positive patients);
- Physical examination (inclusive of head circumference and Tanner stage at W49 & W97);
- Height;
- ECG;
- Exploratory biomarker urine sample collection;
- Exploratory biomarker DBS and plasma sample collection;
- Plasma sample collection for microRNA analyses;
- Urine Hex4 sample collection;
- PedsQL;
- PGIC (patients ≥ 18 years of age at the concerned visit, at W49 and W97 only);
- PFT;
- 6MWT;

- GSGC;
- GMFM-88/GMFCS;
- QMFT;
- HHD;
- IRT call for end of treatment (Week 97 for patients not entering the extended open-label avalglucosidase alfa long-term follow-up phase only).

10.1.7.3 Extended open-label avalglucosidase alfa long -term follow-up phase (pediatric patients enrolling directly in open-label follow-up phase)

10.1.7.3.1 Biweekly

The following assessments will be performed every 2 weeks, starting at W99 and up to 144 additional weeks (W99, W101, W103, W105, W107, W109, W111, W113, W115, W117, W119, W121, W123, W125, W127, W129, W131, W133, W135, W137, W139, W141, W143, W145, W147, W149, W151, W153, W155, W157, W159, W161, W163, W165, W167, W169, W171, W173, W175, W177, W179, W181, W183, W185, W187, W189, W191, W193, W195, W197, W199, W201, W203, W205, W207, W209, W211, W213, W215, W217, W219, W221, W223, W225, W227, W229, W231, W233, W235, W237, W239, W241) or until avalglucosidase alfa is approved in the patient's country, whichever comes first (refer to Appendix C [Section 17.3.4](#) for definition applicable for UK patients):

- IRT contact for treatment kits allocation;
- Vital signs (before, during, and following infusion);
- Infusion of avalglucosidase alfa;
- AE collection;
- Prior/concomitant medications.

10.1.7.3.2 Every 4 weeks (Monthly)

The following assessments will be performed every 4 weeks, starting at W101 and up to 144 additional weeks (W101, W105, W109, W113, W117, W121, W125, W129, W133, W137, W141, W145, W149, W153, W157, W161, W165, W169, W173, W177, W181, W185, W189, W193, W197, W201, W205, W209, W213, W217, W221, W225, W229, W233, W237, W241) or until avalglucosidase alfa is approved in the patient's country, whichever comes first (refer to Appendix C [Section 17.3.4](#) for definition applicable for UK patients):

- IRT contact for treatment kits allocation;
- Vital signs (before, during, and following infusion);
- Body weight (for pediatric patients only);
- Infusion of avalglucosidase alfa;

- Urine pregnancy test (females of childbearing potential only);
- AE collection;
- Prior/concomitant medications.

10.1.7.3.3 Every 12 weeks (Quarterly)

The following assessments will be performed every 12 weeks, starting at W109 and up to 144 additional weeks (W109, W121, W133, W145, W157, W169, W181, W193, W205, W217, W229, W241) or until avalglucosidase alfa is approved in the patient's country, whichever comes first (refer to Appendix C [Section 17.3.4](#) for definition applicable for UK patients):

- IRT contact for treatment kits allocation;
- Vital signs (before, during, and following infusion);
- Infusion of avalglucosidase alfa;
- Body weight;
- Urine pregnancy test (females of childbearing potential only);
- ADAs (with neutralizing antibodies in ADA-positive patients);
- AE collection;
- Prior/concomitant medications.

10.1.7.3.4 Every 24 weeks (every 6 months)

The following assessments will be performed every 24 weeks, starting at W123 and up to 144 additional weeks (W123, W145, W169, W193, W217, W241) or until avalglucosidase alfa is approved in the patient's country, whichever comes first (refer to Appendix C [Section 17.3.4](#) for definition applicable for UK patients):

- IRT contact for treatment kits allocation;
- Vital signs (before, during, and following infusion);
- Infusion of avalglucosidase alfa;
- Body weight;
- Urine pregnancy test (females of childbearing potential only);
- ADAs (with neutralizing antibodies in ADA-positive patients);
- AE collection;
- Prior/concomitant medications;
- Height;
- Hematology, biochemistry, and urinalysis;

- PFT;
- 6MWT.

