- f Vital signs (including heart rate, blood pressure, respiratory rate, temperature and oxygen saturation) are to be assessed prior to infusion, with each infusion rate change (including the start of infusion which is considered as first infusion rate change), at the end of the infusion and at the end of the post-infusion observation period, ie, a total of 7 assessments. Collection windows are ± 15 minutes.
- g Blood samples will be obtained as blood volume permits and will not exceed the blood volume collection limit of <7 mL/kg over an 8-week period. Sampling is prioritized for safety laboratory tests and then exploratory tests.
- h Additional samples may be taken if clinically indicated in the event of IARs.
- i FVC, MIP, and MEP (Additional parameters of respiratory function may be obtained and analyzed as appropriate). Ventilator use status and any change thereof will be recorded on the e-CRF by authorized site personnel.
- j PGIC: Patients who are ≥ 18 years of age at the date of the concerned visit will complete this assessment annually.
- k 12-lead ECG after at least 15 minutes in supine position and prior to receiving IMP.
- l For visits where urine dipstick is required, refer to [Section 9.2.2.2](#) for conditions requiring sending a urine sample to central laboratory.
- Abbreviations: 6MWT = 6-minute walk test; ADA = anti-drug antibody; AE = adverse event; ECG = electrocardiogram; e-CRF = electronic case report form; IAR = infusion associated reaction; IRT = interactive response technology; MEP = maximum expiratory pressure; MIP = maximum inspiratory pressure; PedsQL = Pediatric Quality of Life Inventory; PFT = pulmonary function testing; PGIC = Patient Global Impression of Change

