10.1.5.4 Every 24 weeks (every 6 months)

The following assessments will be performed every 24 weeks, starting at Week 169 and up to 144 additional weeks (W169, W193, W217, W241, W265, W289) or until avalglucosidase alfa is approved in the patient's country, whichever comes first (refer to Appendix C [Section 17.3.3](#) for patients in Canada and [Section 17.3.4](#) for definition applicable for UK patients):

- IRT contact for treatment kits allocation;
- Vital signs (before, during, and following infusion);
- Infusion of avalglucosidase alfa;
- Body weight;
- Urine pregnancy test (females of childbearing potential only);
- ADAs (with neutralizing antibodies in ADA-positive patients);
- AE collection;

- Prior/concomitant medications;
- Height (in pediatric patients only);
- Hematology, biochemistry, and urinalysis;
- PFT;
- 6MWT;
- SF-12 (patients ≥ 18 years of age at screening/baseline);
- EQ-5D-5L (patients ≥ 18 years of age at screening/baseline);
- PDSS/PDIS (patients ≥ 18 years of age at screening/baseline, via an e-diary daily for 2 weeks between visits);
- R-PAct (patients ≥ 18 years of age at screening/baseline).

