10.1.5.5 Every 48 weeks (Yearly) and end of treatment visit

The following assessments will be performed every 48 weeks, starting at Week 193 and up to 144 additional weeks after Week 145 (W193, W241, W289) or until avalglucosidase alfa is approved in the patient's country, whichever comes first (refer to Appendix C [Section 17.3.3](#) for patients in Canada and [Section 17.3.4](#) for definition applicable for UK patients):

- IRT contact for treatment kits allocation;
- Vital signs (before, during, and following infusion);
- Infusion of avalglucosidase alfa;
- Body weight;
- Urine pregnancy test (females of childbearing potential only);
- ADAs (with neutralizing antibodies in ADA-positive patients);
- AE collection;
- Prior/concomitant medications;
- Height;
- Hematology, biochemistry, and urinalysis;
- ECG;
- PFT;
- 6MWT;
- SF-12 (patients ≥ 18 years of age at screening/baseline);
- EQ-5D-5L (patients ≥ 18 years of age at screening/baseline);
- PedsQL (patients < 18 years of age at screening/baseline);
- PDSS/PDIS (patients ≥ 18 years of age at screening/baseline, via an e-diary daily for 2 weeks between visits);

- R-PAct (patients ≥ 18 years of age at screening/baseline);
- PGIC (patients ≥ 18 years of age at the concerned visit).

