10.1.7.3.5 Every 48 weeks (Yearly) and end of treatment visit

The following assessments will be performed every 48 weeks, starting at W147 and up to 144 additional weeks (W147, W193, W241) or until avalglucosidase alfa is approved in the patient's country, whichever comes first (refer to Appendix C [Section 17.3.4](#) for definition applicable for UK patients):

- IRT contact for treatment kits allocation;
- Vital signs (before, during, and following infusion);
- Infusion of avalglucosidase alfa;
- Body weight;
- Urine pregnancy test (females of childbearing potential only);
- ADAs (with neutralizing antibodies in ADA-positive patients);
- AE collection;
- Prior/concomitant medications;
- Height;
- Hematology, biochemistry, and urinalysis;
- ECG;
- PFT;
- 6MWT;
- PGIC (patients ≥ 18 years of age at the concerned visit).

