2.2 DISPOSITION OF PATIENTS

This section describes patient disposition for both patient study status and the patient analysis populations.

Screened patients will be defined as any patient who has signed the informed consent form.

Randomized patients consist of all patients who have had a treatment kit number allocated and recorded in the IRT database, regardless of whether the treatment kit was used.

Patients treated without being randomized will not be considered as randomized and will not be included in any efficacy population. The efficacy results for the pediatric patients who are enrolled directly in the open-label avalglucosidase alfa long term follow-up phase will be listed.

For patient study status, the total number of patients in each of the following categories will be presented in the PAP clinical study report using summary table:

- Screened patients,
- Screen failure patients and reasons for screen failure (if data is available),
- Nonrandomized but treated patients (if applicable),
- Randomized patients,
- Randomized but not treated patients,
- Randomized and treated patients,
- Number and percentage of patients who did not complete PAP treatment period, with corresponding reasons,
- The total number of patients in each of the following categories will be presented in the ETP clinical study report using summary table.
- Patients who continue into ETP,
- Patients who did not complete ETP,
- Pediatric patients enrolled directly in the open-label avalglucosidase alfa long term follow-up phase
- Number and percentage of patients who did not complete ETP treatment, with corresponding reasons (will be included in final study report only),
- Number and percentage of patients who did not complete ETP follow-up, with corresponding reasons (will be included in final study report only).

For all categories of patients (except for the screened and nonrandomized categories) the summaries will be provided by randomized treatment, and percentages will be calculated using the number of randomized patients as the denominator.

All critical or major deviations potentially impacting efficacy analyses, randomization, and drug-dispensing irregularities, and other major or critical deviations will be summarized in tables giving numbers and percentages of deviations by treatment group.

Additionally, the analysis populations for safety, efficacy, and PK will be summarized in a table by number of patients on the randomized population.

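### For children enrolled directly into open-label treatment, the first 24-weekly and 48-weekly visits (W123 and W147) are listed two weeks late, so the W145 assessments are scheduled again at W147

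*Protocol*

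**What the plan says.** Up to two children may be enrolled straight into open-label treatment. Protocol 8.1 ends their first open-label phase at W97 and starts the extended phase with the infusion at W99. Their extended-phase weeks are set out in 10.1.7.3:

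- **12-weekly (10.1.7.3.3):** "every 12 weeks, starting at W109 and up to 144 additional weeks", listing W109, W121, W133, W145 and on to W241.
- **24-weekly (10.1.7.3.4):** "every 24 weeks, starting at W123 and up to 144 additional weeks", listing W123, W145, W169, W193, W217, W241.
- **48-weekly (10.1.7.3.5):** "every 48 weeks, starting at W147 and up to 144 additional weeks", listing W147, W193, W241.

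The randomised patients' parallel sections read "every 24 weeks, starting at Week 169 and up to 144 additional weeks" (10.1.5.4) and "every 48 weeks, starting at Week 193 and up to 144 additional weeks after Week 145" (10.1.5.5). Their last visit before the extended phase is W145.

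Flow chart 1.2.5.2, for the children's extended phase, gives frequencies but no week numbers.

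For ADA in the children's earlier open-label phase, 10.1.7.2.3 says "monthly through Week 73, then at W97 only". The week list in 10.1.7.2.4 likewise goes from W73 to W97. Flow chart 1.2.5.1 marks ADA at W85 as well as W97, and 9.2.2.7 asks for three-monthly sampling after Week 73.

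**The concern.** Two lists do not follow the interval they state, and in each only the first entry is out of line. Section 10.1.7.3 is the only place in the protocol that gives week numbers for this phase, so a site that follows it will place assessments at W123 and W147. Those weeks sit two weeks after W121 and W145, where the same children already have assessments due.

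What is at stake is burden rather than inference. The repeats include blood draws in children, for whom the flow-chart footnotes say sampling "will not exceed the blood volume collection limit of <7 mL/kg over an 8-week period". Each duplicate pair falls within a single 8-week period, and the protocol gives no reason for the second draw.

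The W85 discrepancy runs the other way: a site that follows the text of 10.1.7.2.3 would omit an ADA sample that the flow chart requires.

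**Working it through.** **Inputs.** The children's last visit before the extended phase is W97, and the first visit in it is W99 (Protocol 8.1). The lists come from 10.1.7.3.2 to 10.1.7.3.5. The comparison lists come from 10.1.5.4 and 10.1.5.5, where the preceding phase ends at W145.

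**Step 1: gaps as listed, starting from W97.**

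- 24-weekly: 123 − 97 = 26; 145 − 123 = 22; then 24, 24, 24, 24.
- 48-weekly: 147 − 97 = 50; 193 − 147 = 46; 241 − 193 = 48.
- 12-weekly: 109 − 97 = 12, and 12 throughout.

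**Step 2: can any single starting point reproduce the lists?**

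| Counted from | Every 24 weeks | Every 48 weeks |
|---|---|---|
| W97 | 121, 145, 169, 193, 217, 241 | 145, 193, 241 |
| W99 | 123, 147, 171, 195, 219, 243 | 147, 195, 243 |
| As printed | 123, 145, 169, 193, 217, 241 | 147, 193, 241 |

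Neither row reproduces the printed lists. Only the first printed entry fits W99 (99 + 24 = 123; 99 + 48 = 147). All the others fit W97.

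**Step 3: which starting point is intended?** The randomised patients' lists count from the last visit of the preceding phase: 169 − 145 = 24 and 193 − 145 = 48. The equivalent visit for the children is W97. Their 4- and 12-weekly lists also contain W121 and W145, and contain neither W123 nor W147. SAP Table 14 has analysis visits at Week 121 and Week 145 and none at 123 or 147.

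**Step 4: what is duplicated.** The 24-weekly list has 12 items. All 12 are also in the 14-item 48-weekly list, which adds ECG and PGIC. So everything due at W145 is due again at W147. Five items are due at every biweekly visit anyway: treatment-kit contact, vital signs, infusion, AEs and medications. The other seven are true repeats after two weeks: body weight, pregnancy test (where applicable), ADA, height, safety laboratory tests, PFT and 6MWT. ADA is also due at W121 (12-weekly) and again at W123 (24-weekly).

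**Step 5: counts per child through W241.**

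- ADA as written: 12 quarterly weeks + W123 + W147 = 14. Corrected: 12.
- Safety laboratory sets as written: W123, 145, 147, 169, 193, 217, 241 = 7. Corrected: W121, 145, 169, 193, 217, 241 = 6.

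**Step 6: ADA before W97.** Three-monthly sampling after W73 gives 73 + 12 = 85 and 85 + 12 = 97. That agrees with flow chart 1.2.5.1 and with 9.2.2.7. Sections 10.1.7.2.3 and 10.1.7.2.4 omit W85.

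**Step 7: were these visits still ahead?** The rationale for amended protocol 06 (04 February 2022) says the last patient enrolled was a child entering the open-label period in August 2020. Assume the first infusion was that month. W123 is then (123 − 1) × 7 = 854 days later, between early December 2022 and early January 2023. W147 is (147 − 1) × 7 = 1,022 days later, between late May and mid-June 2023. Both dates come after the amendment.

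**The case against.** The case against making much of this is fair on several counts.

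- **Scale.** At most two children are involved. They are not randomised, and SAP 2.2 says efficacy results for those "enrolled directly in the open-label avalglucosidase alfa long term follow-up phase will be listed". The extended phase may also end at local approval before W123 or W147 is reached. All of this stands, and it is why the point is minor.
- **Recoverable intent.** The section titles, flow chart 1.2.5.2 and all the later entries show what was meant, and the documents do not say how sites resolved the conflict. That is true. But a site should not have to infer a schedule from text that prints a different one.
- **Blood-volume cap.** The cap limits sampling whatever the schedule says, so a duplicate draw should not breach it. This stands. The issue is needless burden and volume, not a safety breach.
- **Visit windows.** The ±14-day window lets one PFT and 6MWT session serve both W145 and W147. The ±7-day safety windows meet at one point only, W145 + 7 days = W147 − 7 days, and no infusion visit is scheduled there. So the counts of 14 and 7 are scheduled numbers on nominal dates, not unavoidable draws.
- **W85 is a separate matter.** It concerns an earlier phase and an omission rather than a duplicate. That is correct. It is included because it affects the same children and can be fixed in the same edit. The flow chart table extracts poorly, but the 4-weekly biochemistry row in the same block supports reading the ADA mark as W85.

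**Conclusion.** The concern holds. W123 and W147 are each two weeks late, and W121 and W145 are the weeks that fit the stated intervals and every comparable list. As written, each child who reaches those weeks has two extra ADA draws and one extra safety laboratory set scheduled. Height, PFT and 6MWT are also repeated at W147, although one PFT and 6MWT session can cover both weeks.

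The size is small: up to two children, and only those still on study at W123 or W147. The randomised comparison, sample size and power are untouched, and no efficacy result is lost. The counts assume visits on their nominal dates. The statement that the visits were still ahead at amendment 06 assumes a first infusion in August 2020 and continued participation. It is still worth correcting, because the extra draws serve no stated purpose and the change costs almost nothing.

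**What to change.** 1. In 10.1.7.3.4, change W123 to W121 in both the start week and the list, giving W121, W145, W169, W193, W217, W241.
2. In 10.1.7.3.5, change W147 to W145 in both places, giving W145, W193, W241. ECG and PGIC then move to W145 with the rest.
3. In 10.1.7.2.3 and 10.1.7.2.4, state that ADA after W73 is sampled at W85 and W97. Make clear that W85 is for ADA only and does not bring in the other 12-weekly assessments.

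The cost is two week numbers and one ADA phrase. No visits are added. Per child, the change removes two scheduled ADA draws and one laboratory set. The W85 sample is already on the flow chart, so it is not a new procedure.

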10.1.7.3.5 Every 48 weeks (Yearly) and end of treatment visit

The following assessments will be performed every 48 weeks, starting at W147 and up to 144 additional weeks (W147, W193, W241) or until avalglucosidase alfa is approved in the patient's country, whichever comes first (refer to Appendix C [Section 17.3.4](#) for definition applicable for UK patients):

- IRT contact for treatment kits allocation;
- Vital signs (before, during, and following infusion);
- Infusion of avalglucosidase alfa;
- Body weight;
- Urine pregnancy test (females of childbearing potential only);
- ADAs (with neutralizing antibodies in ADA-positive patients);
- AE collection;
- Prior/concomitant medications;
- Height;
- Hematology, biochemistry, and urinalysis;
- ECG;
- PFT;
- 6MWT;
- PGIC (patients ≥ 18 years of age at the concerned visit).

10.1.7.4 End of study (pediatric patients enrolling directly in the open-label follow-up phase)

The following assessments will be performed at the end of study visit/contact (2 to 4 weeks after last infusion):

- AE collection;
- Prior/concomitant medications.

10.1.8 Follow-up

- The Investigator should take all appropriate measures to ensure the safety of the patients, notably he/she should follow-up the outcome of any AEs (eg, clinical signs, laboratory values or other) until the return to normal or consolidation of the patient's condition.

- All AEs documented at a previous visit/contact that are designated as ongoing will be reviewed by the Investigator at subsequent visits/contacts.
- In case of any SAE, the patient must be followed up until clinical recovery is complete and laboratory results have returned to normal, or until outcome has been stabilized. This may imply that follow-up may continue after the patient has left the clinical trial and that additional investigations may be requested by the monitoring team. The Investigator will ensure that follow-up includes further investigations consistent with appropriate medical management and patient consent to elucidate the nature and/or causality of the AE.
- In case of any SAE or non-serious AE brought to the attention of the Investigator at any time after cessation of the IMP and considered by him/her to be caused by the IMP with a reasonable possibility, this should be reported to the monitoring team.
- The Investigator will provide follow-up information for any SAE to the Sponsor as soon as it is available. The Sponsor or regulatory authorities may request additional information regarding an SAE.
- For this study, the on-treatment period will be defined as the period from the time of first dose of IMP to at least 4 weeks after the last administration of the IMP. The on-treatment period may end earlier (ie, 2 weeks after the last administration of IMP) if the patient enrolls in another study or receives commercially available ERT. In this case the follow-up period may be reduced from 4 to 2 weeks. For the purposes of the study, status of ongoing and new AEs will be assessed 4 weeks after the last infusion, or for patients who discontinue early, after their last completed study visit. Any new AE or SAE that occurs during the 4-week follow-up period will be reported/collected in the clinical database.
- In exceptional circumstances, if a visit is missed during the course of the study, the following should be followed:
 - If safety assessments/procedures should have been performed during that missed visit, they will be performed at the next visit, even if none was planned, using unscheduled lab kits for any lab samples.
 - If efficacy assessments/procedures should have been performed during that missed visit (ie, V9/Week 13, V15/Week 25, V21/Week 37, V27/Week 49, V34/Week 61, V40/Week 73, V52/Week 97, V64/Week 121 [not applicable for pediatric patients aged 3 to <18 directly enrolled in the open-label long-term follow-up phase], V76/Week 145 [not applicable for pediatric patients aged 3 to <18 directly enrolled in the open-label long-term follow-up phase], or any every 24 weeks visit of the extended open-label long-term follow-up phase), they will be performed at the earliest possible date (which might exceed the authorized window) and will still be associated with the visit that was missed (see CRF completion guidelines for details regarding the CRF completion in this case). In these instances, this will not be considered a deviation but should be clearly documented in the patient's file. Refer to [Section 9.1.1](#) for details on PFT when missed.
- Visits that are longer due to multiple assessments or procedures (eg, motor assessments and multiple questionnaires) may be carried out over 2 days. In any case, IMP

administration should be the last procedure and the appropriate time needed for post-infusion surveillance will be taken into account.

- Postbaseline PFT should meet the ATS/ERS 2005 quality standards. However, if no acceptable efforts can be recorded during the upright position PFT with up to 8 efforts, an additional PFT may be scheduled as soon as possible no later than 45 days after this failed planned test, if this is feasible for the patient. The highest acceptable effort will be kept in the database.
- In addition, if the patient did not perform the PFT at a planned visit, the patient should be reminded to perform the PFT test as soon as possible no later than 45 days after the missed test, if it is feasible for the patient to perform the test within this period.

